	
his/her supplementation must be completed before 1h before bedtime.
 
2. Biological sample collection:
 
The remaining post-test serum samples need to be collected for metabolomics analysis from patients on day 1 of admission, postoperative day 6, postoperative 1 month, postoperative 3 months, and postoperative 6 months.
 
3. Clinical data collection:
 
1) General information: gender, age, height, weight, BMI, ICG 15min retention time, name of surgery, duration of surgery, blood loss, blood transfusion, tumor stage, NRS2002, GLIM malnutrition assessment (diagnostic) criteria diagnosis.
 
2) Nutritional indicators: Nutritional indicators such as serum albumin (ALB), prealbumin (PA), transferrin (TRF), and total serum protein (TP) were collected from patients on the 1st day of admission, the 6th postoperative day, 1 month postoperatively, 3 months postoperatively, and 6 months postoperatively.
 
(3) Liver function indexes: Liver function indexes such as alanine aminotransferase(ALT), alanine transaminase(AST), γ-glutamyltransferase (GGT), cholinesterase (CHE), and total bilirubin (TBIL) were collected on the 1st day of admission, the 6th postoperative day, 1 month postoperatively, 3 months postoperatively, and 6 months postoperatively.
 
(4) Clinical outcome: collect the patients' postoperative clinical outcome indicators, such as: postoperative complication rate, recurrence-free survival, and quality of survival.
 
(5) Medical costs: collect the total cost of the patients' hospitalization, the cost of anti-infective drugs, and the cost of albumin during hospitalization.

Evaluation of the	
Indicators of effectiveness evaluation
 
Main efficacy indicators: serum albumin (ALB)
 
Secondary efficacy indicators: serum prealbumin (PA), alanine

efficacy of treatment	aminotransferase (ALT), azelaic transaminase (AST), cholinesterase (CHE), total bilirubin (TBIL), total hospitalization costs, relapse-free survival, and quality of life
	
Safety evaluation indicators
 
Incidence of gastrointestinal symptoms such as abdominal distension, diarrhea, nausea and vomiting, incidence of postoperative complications, and length of postoperative hospitalization

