6.5 Clinical outcomes

The time of occurrence of postoperative complications and symptoms of the subjects were recorded daily during the patients' hospitalization, and the recurrence-free survival and quality of survival were followed up at 1 month, 3 months, and 6 months postoperatively.

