Adverse events (AEs), all adverse medical events that occur after a subject receives a late-night snack, which can be manifested as symptoms signs, illnesses, or abnormal laboratory tests, but are not necessarily causally related to the late-night snacks.

Serious Adverse Event (SAE), an adverse medical event such as death, life-threatening, permanent or severe disability or loss of function, subject requiring hospitalization or prolonged hospitalization, and

congenital anomalies or birth defects that occur after a subject receives late-evening snacks.

The investigator will closely observe or follow up the various reactions of the patients after performing the LES in order to detect adverse events or serious adverse events in a timely manner, and all adverse events such as bloating, diarrhea, etc., reported by the subjects or observed by the investigator during the period from enrollment to the end of the study or early withdrawal from the study must be documented in the medical record or CRF, including laboratory and ancillary investigations, and should include, at a minimum, the name of the AE, its occurrence time (to the nearest minute), end time (to the nearest minute), degree and frequency of episodes, whether or not treatment was corrected, the course of treatment and regression if treatment was documented, and the causal relationship to the study. All medical documentation related to the adverse event must be recorded in the original documentation, including copies of requests for laboratory tests and reports of test results. The name of the investigator must be signed and dated (to the nearest minute) on the original documents and written reports.

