A data safety monitoring program will be established for clinical studies according to the level of risk. All adverse events will be recorded in detail, appropriately handled and followed up until properly resolved or stabilized, and serious adverse events and unintended events, etc., will be reported to the Ethics Committee, the competent authority, the sponsor, and the drug regulatory authority in a timely manner according to the regulations; the principal investigator will conduct a cumulative review of all adverse events on a regular basis, and convene a meeting of the investigators to assess the risks and benefits of the study, if necessary; the injuries or discomfort is no more likely and no greater in magnitude than that encountered in daily life or than that of a routine examination, and that data and safety monitoring can be accomplished by the principal investigator.

10. Statistical processing

应用 SPSS26.0 统计软件对临床数据进行描述性统计，符合正态分布的计量资料以均数±标

准差($\bar{x} \pm s$)表示, 组间采用 t 检验, 不符合正态分布的计量资料以中位数(四分位间距) [M(IQR)] 表示, 组间采用 Mann-Whitney U 检验。计数资料用百分比[n(%)]表示, 组间比较采用卡方检验, $P<0.05$ 为有显著性统计学意义。采用 STATA12.0 中的 Kaplan-Meier 法计算各组复发率及无复发生存期, log-rank 检验进行组间比较。SPSS26.0 statistical software was applied to carry out descriptive statistics of the clinical data, and the measurements that conformed to normal distribution were expressed as mean \pm standard deviation ($\bar{x} \pm s$), and t-test was used between the groups, and the measurements that did not conform to normal distribution were expressed as median (inter-quartile spacing) [M(IQR)], and Mann-Whitney U-test was used between the groups. Count data were expressed as percentages [n(%)], and the chi-square test was used for between-group comparisons, with $P<0.05$ considered statistically significant. The Kaplan-Meier method in STATA 12.0 was used to calculate the recurrence rate and recurrence-free survival in each group, and the log-rank test was used for between-group comparisons.

11. Ethical principles of clinical research

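### Section 8 ties adverse and serious adverse events to receiving the snack, so read literally a compliant control cannot have one, although recording runs from enrollment

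*Combined protocol and SAP*

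**What the plan says.** Section 8 (Adverse Events Watch) makes four statements that bear on this point.

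- Adverse events are "all adverse medical events that occur after a subject receives a late-night snack". A causal link is expressly not required.
- Serious adverse events are introduced by a list (death, threat to life, disability, hospitalization and so on) that ends "congenital anomalies or birth defects that occur after a subject receives late-evening snacks".
- Surveillance: "The investigator will closely observe or follow up the various reactions of the patients after performing the LES in order to detect adverse events".
- Recording: events that subjects mention or the investigator notices "during the period from enrollment to the end of the study or early withdrawal from the study must be documented". This sentence is not limited to one group.

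Section 9 (Data security monitoring) then relies on these terms. It says that "serious adverse events and unintended events, etc., will be reported to the Ethics Committee" and other bodies, and that "the principal investigator will conduct a cumulative review of all adverse events on a regular basis". It offers no definition of its own.

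Sections 3.2 and 5.1 assign the control group no food in the hour before bedtime. The snack belongs to the test group, and its staged schedule first lists it on postoperative day 2.

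**The concern.** In a two-group study the safety question is whether events are more frequent with the intervention than without it. That needs one definition, applied over the same period in both groups. Here the event is defined by exposure to the intervention, and controls are not meant to have that exposure.

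At stake are the classification of events, the reporting of serious events to the Ethics Committee, and the principal investigator's risk-benefit review. After hepatectomy, serious events are plausible in either group for reasons unrelated to a snack. If control events are not classified as adverse events, background surgical morbidity cannot be set against what is seen in snack takers. The study is open and patients choose their group, so staff who must decide which sentence governs will know each patient's group when they decide.

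**Working it through.** The plan gives no figure to reproduce here, so the check is a comparison of texts followed by a count.

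1. **Who can meet the adverse event definition?** The condition is receipt of a snack. A control who follows the regimen never receives one and so can never qualify. A control who breaks the regimen could: section 4.4 removes controls only after more than 7 bedtime meals. The synopsis also has a phrase in the control group's postoperative text about continuing the snack regimen, which section 3.2 does not repeat. The literal gap therefore concerns compliant controls.

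2. **Does the serious event definition have the same limit?** The snack clause comes at the end of the list. Its natural reading governs the whole list, in parallel with the adverse event definition just before it. Grammatically it could attach only to the last item, congenital anomalies. On that narrower reading a control's death could be a serious adverse event without being an adverse event, which would be a new inconsistency.

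3. **Does the recording window repair this?** The window opens at enrollment and covers all subjects, but what it records is the adverse event, a term already limited by snack receipt. Two sets of events lie inside the window and outside the definition:
   - all events in compliant controls;
   - test-group events between enrollment and the first snack. If the first snack is on postoperative day 2, as the staged schedule suggests, this takes in the preoperative stay, the operation and postoperative day 1.

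4. **Is there another definition elsewhere?** No. The rest of section 8 (grading, follow-up, relatedness table) and section 9 reuse the terms.

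5. **How many subjects?** Planned controls: 53 of 106, and 53/106 = 50%. At the pre-dropout size in section 3.1 the share is the same: 44/88 = 50%.

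6. **What is captured by other routes?**
   - Section 3.2: the data form includes recurrence and survival, so a control's death is recorded.
   - Section 6.5: complications and symptoms are recorded daily in hospital, and "the recurrence-free survival and quality of survival were followed up at 1 month, 3 months, and 6 months postoperatively".
   - Section 7.2: complications have their own definitions. The gastrointestinal item starts from nutritional support, with no snack condition and no cutoff at discharge.
   - Section 8: clinical manifestations are to be evaluated in subjects during the study, and each subject receives an investigator contact for reporting symptoms.
   - Section 9: unintended events are reportable as well as serious ones.
   - Quality-of-life questionnaire: at least one digestive item, on early fullness.

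   None of these is limited to snack takers. None says that a control event is an adverse or serious adverse event.

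**The case against.** The best reply is that the intent is clear and the effect small. Recording runs from enrollment without a group limit. Section 8 also judges pre-existing conditions against the state before joining the study, not before the first snack. Both suggest that the sponsor meant to cover everyone and worded the definition badly. The routes in step 6 mean that many control events will be written down anyway. This stands, and it is why the point is a wording defect and not a failure of safety monitoring. It does not remove the conflict, because the two definitions and the surveillance sentence all use the snack trigger and nothing overrides them.

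A reader might infer three stronger conclusions. The documents do not support them.

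- *After discharge, gastrointestinal events are sought only in snack takers.* The synopsis lists "Incidence of gastrointestinal symptoms such as abdominal distension, diarrhea, nausea and vomiting" as a safety indicator without limiting it to one group. The section 7.2 definition, the section 8 evaluation of clinical manifestations and the symptom contact also apply to controls.
- *The Ethics Committee and the principal investigator will see one group only.* Section 9 also reports unintended events, which have no snack condition, and the serious-event sentence has a second reading. The most that can be said is that these reviews could lack a control comparator.
- *The plan will produce falsely significant harm.* It is true that 4 events against 0 at 53 per group gives an uncorrected chi-square of 106 × (4 × 53)² / (53 × 53 × 4 × 102) = 4.157, p = 0.041. But the plan names no between-group test of section 8 adverse events, and the general chi-square rule for count data does not single them out. A control count of zero would also require every other route to fail. No false-positive rate should be claimed.

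**Conclusion.** The concern holds as an internal inconsistency in section 8, worth correcting at low priority. Read literally, compliant controls (half of planned enrollment) cannot contribute an adverse event, and on the natural reading cannot contribute a serious one. Pre-snack events in the test group are excluded in the same way. The practical consequence is possible, not certain: classification, serious-event reporting and cumulative review could proceed without a control comparator if staff apply the definition as worded.

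This rests on two assumptions: that the trailing clause governs the whole serious-event list, and that controls keep to their regimen. How many control events would go unclassified cannot be estimated from the documents. The albumin endpoint, in-hospital complication rates and the section 7.2 gastrointestinal definition do not depend on the snack trigger.

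**What to change.** Reword three sentences in section 8:

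- **Adverse event:** any untoward medical event in an enrolled subject of either group, from enrollment to end of study or withdrawal, whether or not related to the snack.
- **Serious adverse event:** an adverse event so defined that meets one of the listed seriousness criteria, over the same population and period.
- **Surveillance:** the investigator observes and follows up subjects in both groups. Relation to the snack is assessed in the test group only.

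Section 9 then needs no change. The cost is the rewording alone, with no added visits, samples or subjects.

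An optional, inexpensive addition is to ask both groups the same short set of gastrointestinal questions at the existing 1-, 3- and 6-month contacts. That would make collection after discharge explicit, but the correction does not depend on it.

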Treatment plan	
Patients who were admitted to the Department of Hepatobiliary Pancreatic Surgery of Drum Tower Hospital affiliated to Nanjing University School of Medicine from February 2024 to January 2025 were selected and screened for enrollment according to the admission criteria. The grouping was not randomized and blinded, and all patients were enrolled according to their individual wishes and divided into a test group (53 cases) and a control group (53 cases). The purpose of the study, the content of the investigation were explained to the patients or their families at the time of admission, the principle of confidentiality was informed to reduce the concerns of the respondents, and the subjects were included in the study after signing an informed consent form after obtaining their consent.
 
1. Treatment programs
 
All patients were screened for nutritional risk within 24h of admission using NRS 2002, nutritional assessment using PG-SGA, and malnutrition diagnosis using GLIM malnutrition assessment (diagnosis) criteria. A target daily amount of 25-30 kcal/kg was set for the patients. Nutritional management was standardized to ensure a balanced dietary intake in both groups. Nutritional cards were issued to each patient according to his/her intake, and were explained and emphasized at the time of admission and at the time of discharge. Patients were asked to choose different food items on the cards according to their own food preferences and actual situation. The experimental group was required to have late-evening snacks (LES) within

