Statistical methods	
Descriptive statistics were performed on the clinical data, and measures that conformed to normal distribution were expressed as mean±standard deviation ($\bar{x} \pm s$), and t-test was used between groups, and measures that did not conform to normal distribution were expressed as median (interquartile spacing) [M(IQR)], and Mann-Whitney U test was used between groups. Count data were expressed as percentages [n(%)], and the chi-square test was used for between-group comparisons, with $P<0.05$ considered statistically significant. The Kaplan-Meier method in STATA 12.0 was used to calculate the recurrence rate and recurrence-free survival in each group, and the log-rank test was used for intergroup comparison.

Duration of the study	24 months

catalogs

1. Research background	1
2. Research purpose	4
3. Types of Research Designs and Experimental Steps	4
4. Case selection	9
5. Research Methodology and Technical Approach.....	10
6. Observed items and testing time points	12
7. Criteria for evaluating the efficacy of treatment	13
8. Adverse Events Watch.....	14
9. Data security monitoring.....	16
10. Statistical processing	16
11. Ethical principles of clinical research.....	17
12. Reference	17

1. Research background

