3.1 Types of Research Designs

Types of study designs: single-center, prospective cohort studies

Research Center: Drum Tower Hospital, Medical School of Nanjing University

Grouping method: non-randomized, open, enrolled according to patients' wishes

[figure not shown]
Sample size calculation basis and formula:

This study was a single-center prospective cohort study with two groups, the test group and the control group, and the serum albumin level of the study subjects was the primary endpoint outcome indicator observed. Based on the review of previous literature^[28] and reference to the results of the pretest, it was expected that the albumin level before LES intervention was 34.2 ± 3.9 g/L and the albumin level

after LES intervention was 37.5 ± 5.4 g/L, with a two-sided $\alpha=0.05$ and a degree of certainty of $1-\beta=90\%$. Using PASS15 software can be calculated to obtain $n=88$ cases. Based on the 1:1 grouping, 44 subjects were needed in each of the test and control groups, and assuming a 20% subject dropout rate, the final minimum number of subjects needed was 53 in each of the test and control groups, for a total of at least 106 subjects included.

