3.2 Experimental Steps

The specific steps of the study are as follows:

Pre-procedure preparation:

According to the literature research, establish the form of patients' clinicopathological data that need to be collected, including basic information (age, gender, hospitalization number), pre-surgical laboratory examination (nutritional indexes, liver function, renal function, coagulation function, blood routine, tumor markers such as alpha-fetoprotein, etc.), surgical records (tumor location, size, number, intra-operative bleeding, etc.), post-surgical laboratory examination, tumor recurrence and treatment modality and patient survival, etc., as well as the establishment of a dietary matching table, respectively writing the dietary education content of the experimental group and the control group, in order to personalize the guidance of the patient's postoperative diet and the correct understanding of the importance of dietary therapy. A case questionnaire was set up for the enrolled patients, and the relevant data of the enrolled patients were recorded in the form.

Screening and Trial:

Patients who were admitted to the Department of Hepatobiliary Pancreatic Surgery of Drum Tower Hospital affiliated to Nanjing University School of Medicine, from February 2024 to January 2025 and met the enrollment criteria were selected for inclusion in this study. The grouping was not randomized and blinded, and all patients were enrolled according to their individual wishes and divided into a test group (53 cases) and a control group (53 cases). The purpose of the study, the content of the investigation, the principle of confidentiality were explained to the patients or their families at the time of their admission to the hospital to reduce the concerns of the respondents, and the subjects were included in the study after signing the informed consent form with their consent.

1. Treatment program:

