(2) Postoperative: start drinking small amount of water on the 1st postoperative day, over to liquid diet after ventilation, and may over to autonomous semi-liquid diet + oral whole protein enteral nutrition during the day + LES program on the 2nd postoperative day. As the patient's voluntary intake meets 60% of the body's needs, the daytime oral enteral nutrition support can be gradually stopped and the LES program can be continued.

3) Discharge: daily intake needs to be on time according to the LES regimen.

Control group: no more food 1h before bedtime.

(1) Preoperative: same as the test group.

(2) Postoperative: start drinking small amount of water on the 1st postoperative day, over to liquid diet after ventilation, and can over to autonomous semi-liquid diet + oral whole protein type enteral nutrition during the day on the 2nd postoperative day. As the patient's voluntary intake meets 60% of the body's needs, enteral nutrition support can be gradually stopped.

(3) Discharge: Doctors judge whether the patients need to continue nutritional support according to their dietary recovery, and if they do, their nutritional supplementation should be completed before 1h

before bedtime.

2. biological sample collection:

Serum samples remaining after testing were collected from patients for metabolomics analysis.

3.Clinical information collection:

(1) General information collection: gender, age, height, weight, BMI, ICG15min retention time, name of surgery, duration of surgery, blood loss, blood transfusion, tumor stage, NRS2002, PG-SGA, GLIM malnutrition assessment (diagnosis) criteria diagnosis;

(2) Nutritional indicators collection: collect nutritional indicators such as serum albumin (ALB), prealbumin (PA), transferrin (TRF), and total serum protein (TP) on the 1st day of the subject's admission to the hospital, on the 6th day of the postoperative period, at 1 month after the operation, at 3 months after the operation, and at 6 months after the operation.

(3) Collection of liver function indexes: Liver function indexes such as alanine aminotransferase (ALT), alanine grass aminotransferase (AST), γ -glutamyltransferase (GGT), cholinesterase (CHE), and total bilirubin (TBIL) were collected on the first day of hospitalization, the sixth postoperative day, the first postoperative month, the third postoperative month and the sixth postoperative month of the subjects.

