(4) Clinical outcome collection: to collect clinical outcome indicators of subjects after surgery, such as: postoperative complication rate, recurrence rate, recurrence-free survival, quality of life.

5) Medical cost collection: to collect subjects' total hospitalization cost, cost of anti-infective drugs, cost of albumin during hospitalization.

Data analysis:

Descriptive statistics were performed on the clinical data, and the measures that conformed to normal distribution were expressed as mean \pm standard deviation ($\bar{x} \pm s$), and the t-test was used between the groups, and the measures that did not conform to normal distribution were expressed as median (interquartile spacing) [M(IQR)], and the Mann-Whitney U test was used between the groups. Count data were expressed as percentages [n(%)], and the chi-square test was used for between-group comparisons, with $P < 0.05$ considered statistically significant. The Kaplan-Meier method in STATA 12.0 was used to calculate the recurrence rate and recurrence-free survival in each group, and the log-rank test was used for intergroup comparison.

4. Case selection

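### Patients choose their own group, yet primary albumin is compared without adjustment and at no named visit

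*Combined protocol and SAP*

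**What the plan says.** **How groups form.** Section 3.1 gives the grouping method as "non-randomized, open, enrolled according to" the patients' wishes. The treatment plan in the abstract summary says "all patients were enrolled according to their individual wishes and divided into a test group" and a control group, planned at 53 each, and section 3.2 agrees.

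**How they are compared.** Three places give the same rule: the abstract summary ("and t-test was used between groups"), the data-analysis part of section 3.2 ("and the t-test was used between the groups") and section 10 ("and t-test was used between the groups"). In each, a Mann-Whitney U test replaces the t-test for non-normal data, at P<0.05. Section 5.1 adds only chi-square and independent-samples t-tests for clinical outcomes. Nowhere is there covariate adjustment, matching, stratification, a propensity method, a change score or a repeated-measures model.

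**What is primary.** Section 3.1 states that "the serum albumin level of the study subjects was the primary endpoint outcome indicator observed". Section 7.1 also names albumin, again without a visit or summary measure. Section 6.2 collects it on admission day 1, postoperative day 6, and at 1, 3 and 6 months. No multiplicity rule is given.

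**What is available for adjustment.** Section 3.2 collects "name of surgery, duration of surgery, blood loss, blood transfusion, tumor stage, NRS2002, PG-SGA", along with age, gender, BMI, ICG retention and the GLIM diagnosis. Its preparation step adds tumour features and intraoperative bleeding from the surgical records.

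**The concern.** A patient who volunteers for a nightly dietary task may differ from one who declines in nutrition, liver reserve or motivation, and each can bear on later albumin. An unadjusted test has no protection against such differences, whatever their size. Section 2.3 expects group differences in albumin and intends to identify how the snack improves nutrition, so the plan aims at an effect claim that its test cannot support.

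The open visit is a second weakness in the same comparison. The sample size assumes one two-sided 5% test. With four eligible visits and none named, the primary result could be chosen after the data are seen.

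**Working it through.** **The plan's own figure.** Section 3.1 gives 34.2 ± 3.9 and 37.5 ± 5.4 g/L, two-sided alpha 0.05 and 90% power.

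- Difference: 37.5 − 34.2 = 3.3 g/L.
- Root-mean-square SD: √((3.9² + 5.4²)/2) = 4.71.
- SE at 44 per group: 4.71 × √(2/44) = 1.00, and the noncentral t (86 df) gives power 0.901.

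The stated 88 evaluable patients reproduce, for one comparison at 5%. The inputs are before- and after-snack values, so they do not imply a visit either.

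**Confounding that shows in admission albumin.** From the plan: SD 3.9 at admission, 5.4 at follow-up (used for both groups) and 44 per group. Assumed: no true effect, a systematic admission imbalance of 1-2 g/L, and baseline/follow-up correlation r of 0.4-0.6.

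Spurious difference = r × (5.4/3.9) × imbalance. SE = 5.4 × √(2/44) = 1.15.

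| r | Imbalance (g/L) | Spurious difference (g/L) | Share of 3.3 | False-positive rate, one t-test |
|---|---|---|---|---|
| 0.4 | 1 | 0.55 | 17% | 7.6% |
| 0.4 | 2 | 1.11 | 34% | 15.8% |
| 0.6 | 1 | 0.83 | 25% | 11.0% |
| 0.6 | 2 | 1.66 | 50% | 29.7% |

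With the SD of 4.71 behind the sample size, the range is about 8-37%. For scale, chance alone gives an admission difference with SE 3.9 × √(2/44) = 0.83 g/L; the table concerns imbalance that is systematic. In 20,000 simulated trials, the first and last rows gave 7.7% and 30.7% for the t-test, and 5.0% and 4.9% for ANCOVA on admission albumin.

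**Confounding by an unmeasured factor.** Suppose an unmeasured common factor accounts for all of r and for the imbalance.

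- Unadjusted bias = (5.4/3.9) × imbalance = 1.38 to 2.77 g/L, with false-positive rates of about 22% and 67%.
- Adjusted bias = (1 − r) × unadjusted bias.

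| r | Imbalance (g/L) | Bias left after ANCOVA (g/L) | Simulated false-positive rate |
|---|---|---|---|
| 0.4 | 1 | 1.38 × 0.6 = 0.83 | 12% |
| 0.6 | 2 | 2.77 × 0.4 = 1.11 | 21% |
| 0.6 | 1 | 1.38 × 0.4 = 0.55 | 9% |
| 0.4 | 2 | 2.77 × 0.6 = 1.66 | 32% |

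Adjustment removes 40-60% of the bias here, not all of it.

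**Multiplicity.** If any of four visits could count as success, independent tests give 1 − 0.95⁴ = 18.5%. For equal between-visit correlations of 0.3, 0.5, 0.7 and 0.9, simulation gives 17.4%, 15.6%, 13.0% and 9.4%. Keeping all four as primary with Bonferroni (alpha 0.0125 each) would need 59 evaluable patients per group by the normal approximation.

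**Precision.** Variance ratio, adjusted to unadjusted = (1 − r²)/(1 − R²), where R² is the share of group choice that the covariates explain.

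- r = 0.6, R² = 0.1: 0.64/0.90 = 0.71.
- r = 0.4, R² = 0.2: 0.84/0.80 = 1.05.
- r = 0.4, R² = 0.4: 0.84/0.60 = 1.40, where power for 3.3 g/L at 44 per group falls to about 78%.

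The case for adjustment is therefore bias, not precision.

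**The case against.** **Eligibility and shared targets narrow the differences.** Sections 4.2 and 4.3 require Child-Pugh A or B and ECOG 0-2, and exclude cachexia, recent supplements and poor past adherence. Section 3.2 sets the same calorie and protein targets for both groups. This limits the spread but does not balance the groups.

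**The plan calls itself a non-randomised cohort with a preliminary look at mechanism.** True, but it also carries a powered hypothesis of group difference, so the label mitigates little.

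**The generic rule would let admission albumin be compared between groups.** It would. That could reveal an imbalance but would not correct it.

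**The plan never says four tests will be run.** This stands. The documented defect is an unnamed visit, and the 9-17% applies only if any visit may count.

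**The sizes are assumed.** This also stands. The 2 g/L case is about half an SD of 3.9, the SDs are not test-versus-control values, and all the confounding figures cover the t-test branch only. ANCOVA returns to 5% only where admission albumin carries the whole imbalance. The direction does not depend on these choices.

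**Adjustment cannot make the result causal and may cost power.** Correct on both counts. Motivation is just the kind of factor that could remain, and the precision loss is material if covariates predict choice strongly.

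**Conclusion.** The concern holds. Groups are self-selected, every stated between-group test for albumin is unadjusted, and no primary visit is named. Followed exactly, the plan can report patient selection as a snack effect. Under the assumed imbalance and correlation, the spurious difference is 0.55-1.66 g/L and the false-positive rate 8-30% at one visit when admission albumin carries the imbalance. Both are larger when an unmeasured factor does. The unnamed visit could separately raise the error rate to 9-17%. These sizes are illustrations, but the lack of any protection follows from the text alone. Because this is the only planned analysis of the primary endpoint, it should be corrected before data are analysed.

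**What to change.** In section 10, and in the matching text of section 3.2 and the abstract summary:

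- **Primary model.** Specify an ANCOVA of postoperative albumin on group, or a linear mixed model with group, visit and their interaction. Adjust for admission albumin and a short prespecified list, for example age, sex, NRS 2002, one liver-reserve measure (ICG retention or Child-Pugh, not both), tumour stage, extent of resection and intraoperative bleeding. With group that is nine terms if each takes one, 88/9 ≈ 10 patients per term; fewer if stage or resection needs several.
- **Covariate timing.** Use only factors fixed before the snack starts. Section 3.2 first lists the snack on postoperative day 2 but also states the bedtime requirement without a start date. These must be reconciled before surgical covariates are used. Extent of resection has to be derived from the operation name. Transfusion is usable only if recorded as intraoperative.
- **One primary visit.** The sponsor names it before data are seen, as the single 5% comparison. Other visits are reported as estimates with confidence intervals.
- **Sensitivity analysis.** Propensity-score overlap weighting on the same covariates.
- **Interpretation.** State that unmeasured confounding remains and that conclusions are associational.

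The exact model and covariate list are open to choice; some prespecified adjustment is not. The group-specific removal rules in section 4.4 are a separate selection problem that this does not correct.

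The cost is wording and some extra analysis, with no new data or visits. Other visits can no longer be claimed as primary. With one visit, the basis for 44 per group is unchanged, but power would fall if the covariates strongly predict group choice, by an amount the documents do not allow to be computed.
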